10.1.2 Time at risk in subject-years by COVID-19 pandemic period

The time at risk will be determined by COVID-19 pandemic period as defined in [Section 3.11](#).

10.1.2.1 Time at Risk in the pre-COVID-19 pandemic period

Only subjects starting study drug during the pre-COVID-19 pandemic period will have a time at risk calculated during that period.

- For subjects with date of last dose of study drug on or after 11Mar2020:

10Mar2020 – date of first dose + 1

- For subjects who have died on or before 10Mar2020:

Date of death – date of first dose + 1 (If the date of death is later than 140 days following the last dose of BKZ, this rule does not apply).

- For subjects with date of last dose of study drug on or before 10Mar2020 but with the earliest date between (date of last dose + 141) and (date of last clinical contact) on or after 11Mar2020:

10Mar2020 – date of first dose + 1

- For subjects with date of last dose of study drug on or before 10Mar2020 but with the earliest date between (date of last dose + 140) and (date of last clinical contact) on or before 10Mar2020, minimum between:

date of last dose + 141 – date of first dose

date of last clinical contact – date of first dose + 1

10.1.2.2 Time at Risk in the COVID-19 pandemic period

Subjects with study drug period overlapping the COVID-19 pandemic periods will have a time at risk calculated during that period.

- For subjects with date of last dose of study drug on or after 11Mar2020, minimum between:

Minimum (date of last dose + 141, COVID-19 pandemic end date) – maximum of (11Mar2020, date of first dose)

Minimum (date of last clinical contact, COVID-19 pandemic end date) – maximum of (11Mar2020, date of first dose) +1

- For subjects who have died on or after 11Mar2020:

Minimum (Date of death, COVID-19 pandemic end date) – maximum of (11Mar2020, date of first dose) + 1 (If the date of death is later than 140 days following the last dose of BKZ, this rule does not apply).

- For subjects with date of last dose of study drug on or before 10Mar2020 but with the earliest date between (date of last dose + 141) and (date of last clinical contact) on or after 11Mar2020, minimum between:

Minimum (date of last dose+ 141, COVID-19 pandemic end date) – 11Mar2020

Minimum (date of last clinical contact, COVID-19 pandemic end date) – 11Mar2020+1

10.1.2.3 Time at Risk in the post COVID-19 pandemic period

Subjects with study drug period continuing after the COVID-19 pandemic periods will have a time at risk calculated during that period.

- For subjects with date of last dose of study drug on or after the end date of the COVID-19 pandemic period, minimum between:

date of last dose + 141 – maximum of (COVID-19 pandemic end date, date of first dose)

date of last clinical contact – maximum of (COVID-19 pandemic end date, date of first dose) +1

- For subjects who have died on or after *COVID-19 pandemic end date*:

Date of death – maximum of (COVID-19 pandemic end date, date of first dose) + 1 (If the date of death is later than 140 days following the last dose of BKZ, this rule does not apply).

- For subjects with date of last dose of study drug on or before *COVID-19 pandemic end date* but with the earliest date between (date of last dose + 140) and (date of last clinical contact) on or after *COVID-19 pandemic end date*, minimum between:

date of last dose + 141 – COVID-19 pandemic end date

date of last clinical contact – COVID-19 pandemic end date+1

10.2 Adverse events

An AE is any untoward medical occurrence in a patient or clinical investigation subject administered a pharmaceutical product that does not necessarily have a causal relationship with this treatment. An AE can therefore be any unfavorable and unintended sign (including an abnormal laboratory finding), symptom, or disease temporally associated with the use of a medicinal (investigational) product, whether related or not to the IMP.

AEs (including SAEs) are characterized as either non-treatment or treatment emergent according to the following criteria:

- Non-treatment emergent are the events with onset date and time prior to the very first administration of study medication (BKZ or placebo) or after a 140-day period after the final drug administration.
- Treatment-emergent AEs (TEAEs) are those with onset date at or after the very first administration of study medication. The events that emerge within 140 days after the final drug administration, will also be considered as treatment emergent (eg, in the case of premature discontinuation or during the 20-week SFU Period).

The incidence of TEAEs will be summarized descriptively by treatment group, MedDRA primary system organ class (SOC), high-level term (HLT), and preferred term (PT).

AEs will be presented as “number of subjects (percentage of subjects) [number of events]”. In this style of output, “[number of events]” will include all cases of an AE including repeat occurrences in individual subjects, while “number of subjects” will count each subject only once.

Adverse event summaries by SOC, HLT and PT will be ordered alphabetically for SOC and HLT within SOC and in terms of decreasing frequency for PT within HLT in the BKZ treatment group and then similarly by decreasing frequency in the placebo group.

AE summaries by PT will be ordered in terms of decreasing frequency for PT within the BKZ treatment group, and in the event of ties, PT will be sorted alphabetically.

TEAEs will be classified according to their date of emergence.

All summaries will be provided by treatment group on the SS.

10.2.1 Standard AE summaries

Tables for incidence of the following categories of TEAES will be provided:

- TEAEs (Overview)
- TEAEs by SOC, HLT, and PT
- TEAEs by decreasing frequency of PT
- TEAEs above reporting threshold of 5% by PT, by SOC and PT
- TEAEs by maximum intensity
- TEAEs by relationship to IMP
- Related TEAEs by SOC, HLT, and PT
- Related TEAEs above reporting threshold of 5% by PT, by SOC and PT
- TEAEs leading to study discontinuation, by SOC, HLT, and PT
- TEAEs leading to study drug discontinuation, by SOC, HLT, and PT
- Treatment-emergent SAEs (TESAEs) by SOC, HLT, and PT
- TESAEs by relationship by SOC, HLT, and PT
- TEAEs leading to death by SOC, HLT, and PT - deaths will be also be tabulated and listed
- Non-Serious TEAEs above reporting threshold of 5% by relationship by PT

Some selected tables of incidence will include the exposure adjusted incidence rate (EAIR) with associated 95% confidence interval and the exposure adjusted event rate (EAER) (see [Section 10.2.3](#)). The categories of TEAEs concerned are listed below.

- TEAEs by SOC, HLT, PT,
- TEAEs leading to study discontinuation by SOC, HLT, PT,
- TEAEs leading to study drug discontinuation,
- TEAEs by timing of onset relative to ADA_b status by SOC, HLT, PT (on subjects treated with BKZ). This will include columns for the following:
 - TEAEs starting before the first ADA_b positive result (includes ADA_b categories 2 and 5) where TEAEs have occurred before the following events: a) the first positive ADA_b result for subjects in category 2 and b) the first post-Baseline boosted ADA_b titer result for subjects with titer results and the first post-Baseline positive ADA_b result for subjects with positive ADA_b at Baseline with no other samples with titer available for subjects in category 5
 - TEAEs starting on the same date or after the first ADA_b positive result (includes ADA_b Categories 2, 3, 4, 5 and 6) where TEAEs have occurred on or after the following events: a) the first positive ADA_b results for subjects in categories 2, 3, 4 and 6, and b) the first post-Baseline boosted ADA_b titer result for subjects with titer results and the first post-Baseline positive ADA_b result for subjects with positive ADA_b at Baseline with no other samples with titer available for subjects in category 5
 - TEAEs for subjects who are ADA_b negative at all timepoints (includes ADA_b Category 1)
- TEAEs by NAb status (ADA_b negative, NAb positive, ADA_b positive / NAb negative) on subjects treated with BKZ. TEAEs will be sorted by system organ class, high level term and preferred term.

Note: for TEAE by onset relative to ADA_b positivity status and by NAb status, all available ADA_b and NAb data at the time of IA cut-off, respectively, will be utilized to derive the subject-level ADA_b/NAb status categories.

- TESAEs by SOC, HLT, PT.

By-subject listings on all AEs and all deaths will be provided on the ES. AEs leading to study discontinuation will also be listed on the SS. AEs occurring at first study drug administration will also be listed. A glossary listing will also be created for all TEAEs.

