- If the ADAb sample is collected within ± 14 days (inclusive) relative to the visit date at which the drug was administered (or ± 14 days from a scheduled visit at which dosing was not performed), the ADAb result for that sample will be associated with the scheduled visit and summarized accordingly. This will include unscheduled assessments (if a dose was administered at an unscheduled visit). Samples collected outside this window will be excluded from the by-visit ADAb summaries and will be listed only.

The rule above will apply to by-visit summaries only; all other summaries of ADAb status will use all available data (scheduled and unscheduled). This rule will not apply for the ET or SFU visits. Thus, all ADAb data obtained at these visits will be included in the by-visit summaries.

In addition, the anti-BKZ antibody status will be further classified as outlined below:

- **Category 1: Pre ADAb negative – treatment emergent ADAb negative:** Includes subjects who are negative at Baseline and antibody negative at all sampling points post treatment (including SFU), one post-baseline missing/inconclusive sample is allowed for subjects with pre-ADAb negative sample. This group also includes subjects who have missing/inconclusive pre-treatment sample (eg, either missing/inconclusive or insufficient volume) at baseline with all post-Baseline samples as ADAb negative.
- **Category 2: Pre ADAb negative – treatment emergent ADAb positive:** Includes subjects who are negative at Baseline and antibody positive at any sampling point post treatment (including SFU). This group also includes subjects who have a missing pre-treatment sample (either missing or insufficient volume) at Baseline with one or more ADAb positive post-treatment samples.
- **Category 3: Pre ADAb positive – treatment emergent reduced ADAb:** Includes subjects who are positive at Baseline, and antibody negative at all sampling points post treatment (including SFU).
- **Category 4: Pre ADAb positive – treatment unaffected ADAb positive:** Includes subjects who are positive at Baseline and are positive at any sampling point post treatment (including SFU) with titer values of the same magnitude as Baseline (ie, less than a predefined fold difference from the Baseline value). For the purpose of this study, this is set at an increase of less than the validated Minimum Significant Ratio (MSR) of 2.07-fold from Baseline.

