- **Category 5: Pre ADAb positive – treatment boosted ADAb positive:** Includes subjects who are positive at Baseline and are positive at any sampling point post treatment (including SFU) with increased titer values compared to Baseline (greater than or equal to a predefined fold difference increase from Baseline value which is defined within the validation of the assay). For the purposes of this study, this is set at an increase greater than or equal to the validated Minimum Significant Ratio (MSR) of 2.07-fold from Baseline.

Note: For any subject who is positive at Baseline and positive at a post-Baseline time point, but for whom titers are not available to determine treatment unaffected or treatment boosted status, the subject will be considered as treatment boosted (ie, Category 5), assuming no other samples are available.

- **Category 6: Inconclusive:** Includes subjects who have a positive pre-treatment sample and some post-treatment samples are missing, while other post-treatment samples are ADAb negative or missing.
- **Category 7: Total treatment-emergent:** Category 2 and 5 combined: Includes subjects who are pre ADAb negative – treatment emergent ADAb positive (Category 2) and pre ADAb positive – treatment boosted ADAb positive (Category 5).
- **Category 8: Total prevalence of pre-ADAb positivity:** (Categories 3, 4, 5 and 6 combined): Subjects that are tested ADAb positive at Baseline.
- **Category 9: Missing:** Includes subjects who have a negative or a missing/inconclusive pre-treatment sample and some post-treatment samples are missing/inconclusive, while other post-treatment samples are ADAb negative or missing.

All the following analyses will be prepared on the SS:

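### The TEAE-by-ADAb-onset table files pre-boost events of Baseline-positive Category 5 subjects as preceding any positive result, while the same antibody state in Category 4 goes to the opposite column

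*SAP*

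**What the plan says.** SAP Section 10.2.1 (Standard AE summaries) plans a table of TEAEs by timing of onset relative to ADAb status, in BKZ-treated subjects, with EAIR and its 95% CI and EAER. Three columns are defined.

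- The before column: "TEAEs starting before the first ADA_b positive result (includes ADA_b categories 2 and 5) where TEAEs have occurred before the following events". For Category 2 the event is the first positive result. For Category 5 it is "the first post-Baseline boosted ADA_b titer result for subjects with titer results", or the first post-Baseline positive result where no titer is available.
- The on-or-after column: "TEAEs starting on the same date or after the first ADA_b positive result (includes ADA_b Categories 2, 3, 4, 5 and 6"). Here the event is "the first positive ADA_b results for subjects in categories 2, 3, 4 and 6", and Category 5 again uses the boosted titer.
- A column for Category 1, who are negative throughout.

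SAP Section 9.2.1 defines the categories. Category 5: "Includes subjects who are positive at Baseline and are positive at any sampling point post treatment (including SFU) with increased titer values compared to Baseline". Its definition of Category 8 confirms that Categories 3, 4, 5 and 6 together are the subjects who test positive at Baseline. Category 7, the total treatment-emergent group, is Categories 2 and 5.

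**The concern.** A subject who is ADAb positive at Baseline already has a positive result when the first TEAE can start. The before column nevertheless receives events from such subjects, provided that a later sample shows a boost. If no boost follows, events arising in the same antibody state go to the other column.

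The table is meant to show whether adverse events follow antibody formation. Its reference column should hold time without the antibody event of interest, defined in the same way for everyone. As written, the reference column includes events in antibody-positive subjects. The comparison column includes events in subjects who never show a treatment-emergent increase. A safety signal tied to pre-existing antibody, or one tied to seroconversion or boosting, would be harder to see, and the counts and rates would not mean what a reader takes from the labels.

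**Working it through.** The SAP states no figure on this point, so the check sets the category definitions (Section 9.2.1) against the column rules (Section 10.2.1).

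| Category | Baseline state and later course | Date that splits the columns | Before column | On-or-after column |
|---|---|---|---|---|
| 2 | "Includes subjects who are negative at Baseline and antibody positive at any sampling point post treatment (including SFU"); a missing Baseline sample is also allowed | first positive | not yet shown positive | treatment-emergent positive |
| 3 | "Includes subjects who are positive at Baseline, and antibody negative at all sampling points post treatment (including SFU") | first positive, i.e. Baseline | none | all TEAEs |
| 4 | "Includes subjects who are positive at Baseline and are positive at any sampling point post treatment (including SFU) with titer values of the same magnitude"; the increase stays below 2.07-fold | first positive, i.e. Baseline | none | all TEAEs |
| 5 | positive at Baseline, increase of at least 2.07-fold | first boosted titer | Baseline positive, not yet boosted | boosted |
| 6 | positive at Baseline, later samples missing or negative | first positive, i.e. Baseline | none | all TEAEs |

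**Step 1: the before column against its label.** TEAEs start at or after first dose (Section 10.2). Category 5 is positive at Baseline, so a Category 5 TEAE cannot precede the first positive result. The label and the rule conflict for this category.

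**Step 2: same state, opposite columns.** Category 4 and pre-boost Category 5 are both Baseline positive and not boosted. The first goes entirely to on-or-after and the second to before. Only a later sample separates them. That sample may be the SFU sample, since the definitions include SFU. Section 4.3.1 re-runs all analyses with new SFU data. A Category 4 subject whose SFU sample is boosted would become Category 5, and the TEAEs that began before that sample would move from on-or-after to before. Subjects who enter the OLE have no SFU visit (Section 9.2.1), so this affects only part of the sample.

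**Step 3: does one reading of the clock repair both columns?**
- Any first positive, counting Baseline, as in the first-occurrence table of Section 9.2.1: pre-boost Category 5 events do not belong in before.
- First treatment-emergent or boosted result (Category 7): Categories 3, 4 and 6 never have the event and do not belong in on-or-after.

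Neither reading fits both columns.

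**Step 4: illustration of size.** Apart from the 260 planned BKZ subjects, every input is assumed: 1.5 TEAEs per subject spread evenly over 16 weeks; 25% (65) in Category 2, first positive at Week 8; 5 to 15% (13 to 39) Baseline positive; 30 to 50% of those boosted, at Week 8.

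- Category 2: 65 × 1.5 × 0.5 = 48.75 events in each column.
- Share of the before column from Baseline-positive subjects. Low (5%, 30%): 3.9 × 1.5 × 0.5 = 2.9; 2.9 / (48.75 + 2.9) = 6%. High (15%, 50%): 19.5 × 1.5 × 0.5 = 14.6; 14.6 / (48.75 + 14.6) = 23%.
- Share of the on-or-after column from Categories 3, 4 and 6. Low (5%, 50%): 6.5 × 1.5 = 9.75; 9.75 / (48.75 + 4.875 + 9.75) = 15%. High (15%, 30%): 27.3 × 1.5 = 40.95; 40.95 / (48.75 + 8.775 + 40.95) = 42%.

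Both shares are zero if nobody is positive at Baseline.

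**The case against.** The rule is explicit. Each label is followed by the event that applies to each category, so Categories 1 to 6 can be programmed without ambiguity and no TEAE is lost or counted twice. The boost clock for Category 5 agrees with Category 7 and with the first-occurrence table, which also takes the first boosted result for that category. On this view the before column holds the time before treatment-emergent ADAb in exactly the two categories that develop it, and a footnote would correct the label. The SAP's change log also shows that the category allocation was reviewed. Other outputs allow reconstruction: counts in all nine categories, listings of every ADAb result and titer, and listings of every AE. The proposed extra column would itself pool several states.

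Much of this stands. A reader might infer that the on-or-after column is wrong as well. The documents do not support that: every TEAE of Categories 3, 4 and 6 does follow a positive result, so the column is mixed but not false to its label. A reader might also take the provision for Category 5 at 10% or more of subjects as a sign of the expected size. It is only a display rule for showing Category 5 separately, and the illustration above gives 1.5% (5% × 30%) to 7.5% (15% × 50%), which never reaches it.

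The footnote argument does not stand. Relabelling the before column leaves Categories 3, 4 and 6 in on-or-after under a clock that they never meet, and it leaves Category 4 and pre-boost Category 5 in opposite columns. The split itself changes the counts and rates, so wording alone does not correct it. The extra column does pool states, but its label would be true of every event in it.

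**Conclusion.** The point holds in this form. The before column contradicts its own label for Category 5, and unboosted Baseline-positive time is filed in opposite columns according to a later sample. The on-or-after column pools treatment-emergent antibody with Baseline-positive antibody that was not boosted; that is a weakness of interpretation and not a false label.

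The consequence is limited to one descriptive safety table with EAIR and EAER. No hypothesis test, efficacy endpoint or decision rule depends on it. The actual size cannot be stated, because the SAP gives no Baseline positivity rate. The ranges of 6 to 23% and 15 to 42% show what the chosen inputs imply and are not estimates for this trial. The table should be changed because it exists to relate event onset to antibody status and the change is small.

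**What to change.** In Section 10.2.1, use one clock for the table: the first treatment-emergent or boosted ADAb result, consistent with Category 7.

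- Before: Category 2 TEAEs that start before the first positive sample.
- On or after: Category 2 TEAEs from the first positive sample and Category 5 TEAEs from the first boosted sample, keeping the existing rule for subjects without titers.
- New column, Baseline ADAb positive with no treatment-emergent increase at onset: Categories 3, 4 and 6, and Category 5 TEAEs before the boost.
- The column for Category 1 stays as it is.

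The column labels should state this clock. The cost is a change of SAP wording and one more column in one table, with no new data. The downside is that the new column may have small counts and imprecise rates.

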10.2.2 Exposure duration of AEs

The duration of each AE will be calculated as follows:

$$\text{Duration of AE (days)} = \text{End date of AE} - \text{Start date of AE} + 1$$

For the calculation of duration for AEs with missing start dates, the dates will be imputed as described in [Section 4.2.3](#).

The time since first dose of IMP for each AE will be calculated as follows for all TEAEs:

Time since first dose (days) = Start date of AE – Date of first dose + 1

The time since the most recent dose of IMP for each AE will be calculated as follows for all TEAEs:

Time since the most recent dose (days)
= Start date of AE – Date of most recent dose + 1

Time to first dose and time to most recent dose will not be calculated for pretreatment AEs.

For the calculation of time to first BKZ and time to most recent BKZ dose the same formulas as above will be used but the date of first BKZ dose will be used instead of the date of first dose of IMP. The time to first dose and time to first BKZ dose differs only for those subjects who receive placebo at Baseline after the time they switch to BKZ.

10.2.3 Exposure adjusted incidence rate (EAIR) and exposed adjusted event rate (EAER)

The EAIR is defined as the number of subjects (k) with a specific AE adjusted for the exposure and will be scaled to 100 patient-years:

$$EAIR = 100 \times \frac{k}{\sum_{i=1}^n (T_{Exp(i)})}$$

where n is the total number of subjects and $T_{Exp(i)}$ is the time of exposure for each subject defined as:

- For subjects with the AE: years since first dose of IMP to the first occurrence for the AE of interest at the level of coding evaluated,
- For subjects without the AE: the time at risk in years.

Exact Poisson 95% CIs for incidence rates are calculated using the relationship between the Poisson and the Chi-square distribution (Ulm, 1990; Fay and Feuer, 1997):

$$LCL = \frac{\chi^2_{2k, \alpha/2}}{2}$$

$$UCL = \frac{\chi^2_{2(k+1), 1-\alpha/2}}{2}$$

where k is the number of subjects with a specific AE for the incidence rate of interest and is the basis for the number of the degrees of freedom for the chi-square quantile for the upper tail probability χ^2 .

The EAER will be the number of AEs (N_{AE}) including repeat occurrences in individual subjects divided by the total time at risk scaled to 100 patient-years and calculated using:

$$EAER = 100 \times \frac{N_{AE}}{\sum_{i=1}^n (T_{Risk(i)})}$$

where N_{AE} is the number of AE occurrences, n is the total number of subjects and $T_{Risk(i)}$ is the time at risk in years for each subject.

No CI will be computed for EAER.

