10.2.5 COVID-19 impact

To assess the impact of COVID-19 pandemic on safety, additional summaries and listings will be presented.

For reporting purposes, AEs will be assigned to either Pre-COVID-19, COVID-19, or post-COVID-19 pandemic period by comparing the AE start date (based on imputed date) to the COVID-19 pandemic period dates (AE allocated to a period if it starts during the period):

The following categories of TEAEs will be summarized by MedDRA SOC, HLT and PT, including EAIR and EAER.

- All TEAEs by time of onset relative to COVID-19 pandemic period (pre – during – post) by region and overall,
- All TEAEs leading to study discontinuation and/or permanent withdrawal of study medication by time of onset relative to COVID-19 pandemic period (pre – during – post) by region and overall,
- All Serious TEAEs by time of onset relative to COVID-19 pandemic period (pre – during – post) by region and overall,
- All COVID-19 related TEAEs by treatment group, by region and overall – COVID-19 related TEAEs will be identified by the two preferred terms “Corona virus infection” and “coronavirus test positive” and will include confirmed or suspected COVID-19 infections.

A listing of COVID-19 related AEs will be presented where these AEs are identified as described above. Additionally, the listing of AEs will include a column for COVID-19 relatedness and the time of onset of each AE relative to the COVID-19 pandemic will be included in all AE listings.

For the purpose of calculating EAIR and EAER by COVID-19 pandemic period, the calculation of exposure time at risk presented in [Section 10.1.2](#) will be used. An individual subject may therefore be counted in the denominator for several COVID-19 pandemic periods dependent on whether the subject is still considered at risk on the COVID-19 pandemic start and stop dates. In this case time at risk will be calculated separately for each period.

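### The EAIR confidence limits in SAP Section 10.2.3 are limits for the count k because the factor 100/ΣT_Exp is missing; a secondary point is that the ADAb-timing rates have no split time at risk

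*SAP*

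**What the plan says.** SAP Section 10.2.3 sets out the point estimate in full: "The EAIR is defined as the number of subjects (k) with a specific AE adjusted for the exposure and will be scaled to 100 patient-years". The formula that follows is EAIR = 100 × k / ΣT_Exp. The exposure term depends on whether the subject had the event. Where it occurred, the rule is: "For subjects with the AE: years since first dose of IMP to the first occurrence for the AE of interest". That clock stops separately at each coding level. Where it did not occur, the whole time at risk counts. The interval is introduced by "Exact Poisson 95% CIs for incidence rates are calculated using the relationship between the Poisson and the Chi-square distribution". The lower limit is then printed as the chi-square quantile with 2k degrees of freedom at α/2, divided by 2. The upper limit is the quantile with 2(k+1) degrees of freedom at 1−α/2, divided by 2. The explanatory sentence after the formulas describes the quantile as an upper-tail one. It mentions neither exposure nor the scale of 100. The EAER divides the number of events by the full time at risk and has no interval.

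Section 10.2.1 lists the tables that carry the EAIR with its 95% interval and the EAER, and refers to Section 10.2.3. One of them is "TEAEs by timing of onset relative to ADA_b status by SOC, HLT, PT". Its before column takes ADAb categories 2 and 5. Its on/after column takes categories 2, 3, 4, 5 and 6. A third column holds subjects who are always negative (category 1). Section 10.2.4 also asks for the EAIR with its interval for the safety topics of interest.

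For the COVID-19 periods the SAP does partition time, in Section 10.1.2. Section 10.2.5 says of a subject at risk in several periods: "In this case time at risk will be calculated separately for each period". There is no counterpart for ADAb status.

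**The concern.** A rate per 100 subject-years and an interval for a count are on different scales. A programmer who follows Section 10.2.3 literally would print them side by side in every EAIR table, including serious events, discontinuations and the safety topics. The divisor cannot be supplied once for the whole study: T_Exp stops at the first occurrence at each coding level, so ΣT_Exp differs by SOC, HLT and PT row. With 2:1 allocation the arms also differ in exposure, so their intervals would be mis-scaled by different factors and could not be compared.

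In the ADAb-timing table, subjects in categories 2 and 5 enter both the before and the on/after columns. The only denominators given are first dose to event and whole time at risk. Each column therefore also counts time in which its own events could not occur. This is the table meant to show whether adverse events follow antibody formation.

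**Working it through.** **1. Limits**

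The SAP states no numerical EAIR or interval, so there is no figure to reproduce. The printed formulas were evaluated as they stand, with lower-tail quantiles, and compared with the same limits multiplied by 100/ΣT_Exp.

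Inputs: 260 BKZ and 130 placebo subjects (Section 2.4) and a 16-week treatment period (Section 2.3.1). Assumed exposure is 16 weeks per subject: 130 × 112/365.25 = 39.9 and 260 × 112/365.25 = 79.7 subject-years. Because follow-up may lengthen time at risk, 200 subject-years is added as a range.

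For k = 10 the printed limits are 4.795 and 18.390 at any exposure. At 39.9 subject-years the rescaled limits are 100 × 4.795/39.9 = 12.02 and 100 × 18.390/39.9 = 46.09.

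| ΣT_Exp (subject-years) | k | EAIR | Printed limits | Rescaled limits |
|---|---|---|---|---|
| 39.9 | 5 | 12.53 | 1.62 to 11.67 | 4.07 to 29.24 |
| 39.9 | 10 | 25.06 | 4.80 to 18.39 | 12.02 to 46.09 |
| 39.9 | 40 | 100.25 | 28.58 to 54.47 | 71.62 to 136.51 |
| 79.7 | 10 | 12.55 | 4.80 to 18.39 | 6.02 to 23.07 |
| 79.7 | 40 | 50.19 | 28.58 to 54.47 | 35.86 to 68.34 |
| 100 | 10 | 10.00 | 4.80 to 18.39 | 4.80 to 18.39 |
| 200 | 20 | 10.00 | 12.22 to 30.89 | 6.11 to 15.44 |

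The ratio of printed to rescaled limits is ΣT_Exp/100: 0.40 at 39.9, 0.80 at 79.7 and 2.0 at 200. The estimate lies outside its printed interval in all three rows at 39.9 and in the row at 200. For a common event with 100 subjects affected in an assumed 55 subject-years, the EAIR is 181.8 against a printed 81.4 to 121.6; the rescaled interval is 147.9 to 221.1.

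**2. ADAb timing**

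Take a constant event rate λ unaffected by ADAb, follow-up w = 16 weeks and positivity at time s. A category 2 or 5 subject is exposed to before events for s and to on/after events for w − s, but the denominator is w in both columns. The EAER is then λ·s/w before and λ·(w − s)/w on/after. The EAIR behaves almost the same way.

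A simulation (2,000 replicates, 260 BKZ subjects, 30% turning positive, true rate 100 per 100 subject-years, earlier events not removing a subject from the on/after column) gave these EAIRs:

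| Positive at | Algebra, before / on-after | Simulated, before / on-after | Always negative | Time split, before / on-after |
|---|---|---|---|---|
| Week 4 | 25 / 75 | 25.7 / 72.7 | 100.3 | 99.6 / 100.0 |
| Week 8 | 50 / 50 | 52.6 / 48.5 | 100.1 | 100.8 / 101.2 |
| Week 12 | 75 / 25 | 77.6 / 24.4 | 100.6 | 100.5 / 101.1 |

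True rates of 20 and 200, and 45% turning positive, gave proportionally similar results.

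The simulated on/after column holds only subjects who turn positive during follow-up. Categories 3, 4 and 6 are positive from Baseline and contribute no earlier time. If they supply a share m of the column's person-time, the reported fraction of the true rate is about m + (1 − m)(w − s)/w. At s = 8 that is 0.50 for m = 0 and 0.75 for m = 0.5.

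**The case against.** The target is clear. Section 10.2.3 says the limits are for incidence rates, directly beneath the EAIR formula, so an experienced programmer would probably rescale and standard software may already do so. That makes the repair simple, but the SAP does not say it. A reader might go further and call the printed intervals unrelated to the rate. The documents do not support that: they are wrong by one known factor, ΣT_Exp/100, and at 79.7 subject-years with k = 10 the printed interval still contains the estimate.

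A reader might also infer from the upper-tail wording that the two limits are swapped. Read literally with the printed subscripts it would do that (for k = 10, a lower limit of 17.08 and an upper of 5.49). However, the labels and the subscripts α/2 and 1−α/2 fix the intended order, so this is loose wording and not a second error.

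On ADAb timing, the SAP never says in words that time is left unsplit. The point rests on the general denominator being the only one given, together with the cross-reference to Section 10.2.3. Two stronger readings are tempting. One is that both columns report half the true rate. That holds only for category 2 and 5 subjects who turn positive midway; categories 3, 4 and 6 dilute the on/after bias, and the mix is unknown. The other is that the bias would hide a safety signal. With no true effect, positivity at Week 4 shows about 26 before and 73 on/after, which creates one. At Week 12 the pattern reverses.

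**Conclusion.** The interval formulas are wrong as written. The missing factor is visible on the page and needs no assumption about exposure; only the sizes quoted above depend on the assumed subject-years. The EAIR point estimates are not affected by this.

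The ADAb-timing point stands as secondary. For category 2 and 5 subjects the defined denominators understate the EAIR and EAER in both columns, by an amount set by when they turn positive. The before column consists entirely of such subjects and the on/after column only partly. The always-negative column and the baseline-positive categories 3, 4 and 6 are not affected. The sizes assume a constant rate, 16 weeks of follow-up and a single seroconversion week.

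All of these are descriptive safety analyses. The testing hierarchy in Section 4.5 does not use them.

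**What to change.** In Section 10.2.3, replace the limits with:

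- LCL = 100 × χ²(0.025; 2k) / (2 × ΣT_Exp), with LCL = 0 when k = 0;
- UCL = 100 × χ²(0.975; 2(k+1)) / (2 × ΣT_Exp).

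Use the same ΣT_Exp as the EAIR in that row, and reword the explanatory sentence to say lower-tail quantiles.

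For the ADAb-timing table in Section 10.2.1, split each category 2 and 5 subject's time at risk at the date of the first positive result or, for category 5, the date that the section already uses to classify the event. Use the time up to that date for the before column and the time from it for the on/after column, for both EAIR and EAER, on the model of Section 10.1.2. Also state whether a subject whose first event preceded positivity remains at risk in the on/after EAIR column; Section 10.1.2 splits time only and does not settle this.

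The cost is two formula lines, one reworded sentence, one derived time variable and one stated rule. No new data are needed.
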